7.8 Long term follow-up assessments

N/A

7.9 Qualitative assessments

N/A

7.10 Withdrawal criteria

Participants will be withdrawn from the trial if:

- 1) They no longer wish to continue in the study and withdraw consent
- 2) They experience a serious adverse event
- 3) They experience an adverse event not related to the study medication that requires them to be withdrawn (e.g. they develop renal or hepatic impairment).

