2.1 Assessment and management of risk

Risks related to metformin

The side effects of metformin are mainly gastrointestinal. The relevant summary of product characteristics (SmPC) lists gastrointestinal disorders, such as nausea, vomiting, diarrhoea, abdominal pain and loss of appetite, as very common (frequency $>1/10$). It states that these side effects 'occur most frequently during initiation of therapy and resolve spontaneously in most cases.' Taste disturbance is listed as a common side effect (frequency $>1/100$). All other side effects are described as very rare ($<1/10,000$) or not known (cannot be estimated from available data). In accordance with the SmPC, to minimise gastrointestinal effects as far as possible, the study tablets will be administered after meals, and the dose will be escalated gradually to the target dose.

Hypoglycaemia:

Metformin does not induce low blood sugar levels (hypoglycaemia) when used as the sole glucose-lowering therapy in diabetic patients. It does not exert a hypoglycaemic action in non-diabetic patients unless taken in overdose. Even in the setting of overdose, hypoglycaemia has not been seen with metformin doses up to 85g. As diabetes is an exclusion criterion, the use of other oral glucose-lowering agents will not be permitted in this study.

Although not listed in the SmPC, it is suggested that there may be a risk of hypoglycaemia if metformin is administered in the setting of malnutrition, inadequate caloric intake, or excessive alcohol consumption. Therefore these will be exclusion criteria in this study.

Lactic acidosis:

A predecessor of metformin - phenformin - has been associated with lactic acidosis. However a systematic review published in 2010 evaluated the risk for lactic acidosis in type 2 diabetic patients taking metformin and showed no cases of fatal or nonfatal lactic acidosis in 347 prospective trials and cohort studies with more than 70,490 patient-years of metformin use. The authors concluded that there is no evidence that metformin is associated with an increased risk of lactic acidosis (6).

Metformin and COPD

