6.2 Exclusion criteria

Diagnosis of diabetes irrespective of treatment

Diabetes diagnosed on screening bloods

History of hepatic/renal impairment or hepatic/renal impairment diagnosed on screening bloods

Excessive alcohol intake (>21 units/week in males and >14 units in females)

BMI < 18.5kg/m²

Taking metformin irrespective of indication

History of allergy or hypersensitivity to metformin or hypersensitivity or intolerance to any of the placebo compounds

Pregnancy or breastfeeding

Unable to provide informed consent

Any contraindication for Metformin treatment as detailed in Metformin SmPC including:

Acute conditions with the potential to alter renal function such as dehydration, severe infection, shock

Acute or chronic disease which may cause tissue hypoxia such as cardiac or respiratory failure, recent myocardial infarction, shock

Any type of acute metabolic acidosis

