8.6 Dosage schedules

The IMP will be commenced at a dose of 500mg twice daily. After 1 week it will be increased to 1000mg twice daily.

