8.7 Dosage modifications

N/A

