9.8 Reporting urgent safety measures

If any urgent safety measures are taken the CI/Sponsor shall immediately and in any event no later than 3 days from the date the measures are taken, give written notice to the MHRA and the relevant REC of the measures taken and the circumstances giving rise to those measures.

9.9 The type and duration of the follow-up of participants after adverse reactions.

Any SUSAR will be reported to the Sponsor irrespective of how long after IMP administration the reaction has occurred until resolved.

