13.5 Protocol compliance

Prospective, planned deviations or waivers to the protocol will not be allowed. Accidental protocol deviations will be adequately documented on the relevant forms and reported to the CI and Sponsor immediately.

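### Section 7.10 omits non-serious drug-related adverse events from its investigator-led withdrawal criteria, and no routine rule elsewhere says when to hold or stop study drug for them

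*Combined protocol and SAP*

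**What the plan says.** All references are to the combined protocol and SAP.

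Section 7.10 gives three grounds for withdrawal: the participant withdraws consent; the participant has a serious adverse event, with no condition on cause; or "They experience an adverse event not related to the study medication that requires them to be withdrawn". The example attached to the third ground is renal or hepatic impairment.

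Section 8.6 starts everyone at 500 mg twice daily and continues: "After 1 week it will be increased to 1000mg twice daily". Section 8.7, headed "Dosage modifications", contains only N/A.

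Section 2.1 reports that the product characteristics list "nausea, vomiting, diarrhoea, abdominal pain and loss of appetite, as very common" (more than 1 in 10), and that these effects "occur most frequently during initiation of therapy and resolve spontaneously in most cases". Section 6.2 includes among the metformin contraindications at entry "Acute conditions with the potential to alter renal function such as dehydration, severe infection, shock".

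Section 13.5 states: "Prospective, planned deviations or waivers to the protocol will not be allowed".

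**The concern.** A withdrawal rule for a drug trial should first cover harm from the drug. Criterion 3 covers the opposite class. Its own example makes the wording look accidental: renal or hepatic impairment is an exclusion under 6.2 and a reason to stop metformin whatever caused it.

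The omitted events are the ones the protocol expects. A participant with drug-related vomiting or diarrhoea may become dehydrated, a state that 6.2 treats as a contraindication at entry. The protocol does not say what should happen to study drug if that state arises during treatment. What is at stake is participant safety and consistent handling: different clinicians could continue, pause or stop the drug in the same situation, each without a written rule.

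**Working it through.** The claim is about text, and the plan states no figure to reproduce. The check has three steps.

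**1. Which 7.10 ground reaches which event?**

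| Event | Criterion 1 (consent) | Criterion 2 (serious event) | Criterion 3 |
|---|---|---|---|
| Serious, related | participant's choice | yes | not needed |
| Serious, unrelated | participant's choice | yes | not needed |
| Non-serious, unrelated | participant's choice | no | yes |
| Non-serious, related | participant's choice | no | **no** |

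Only the last row has no investigator-led ground.

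**2. Does another section close the gap?**

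- 8.6 and 8.7: a fixed step up, and no modification rule.
- 8.8: metformin is stopped around iodinated contrast imaging. The trigger is the procedure, not an adverse event.
- 8.9: closer renal monitoring if an interacting medicine is started. No action on study drug.
- 8.11: a compliance limit for staying in the trial. Not an adverse-event rule.
- 9.3: the action taken is recorded for each reaction. This is a data field and does not say which action.
- 9.4: the Chief Investigator has clinical oversight. No hold or stop rule follows from it.
- 9.7: the Chief Investigator decides on withdrawal, for overdose only.
- 9.8: urgent safety measures are possible, but the regulator and ethics committee need written notice "no later than 3 days from the date the measures are taken". That is not a routine route for a common, usually reversible event.

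Monthly examination and blood tests (7.7), emergency unblinding (7.5) and provision of the product characteristics (8.3) help to detect or judge an event. None states an action on study drug.

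**3. Size**

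Inputs: 40 participants (10.1), all due metformin in one period of the cross-over; gastrointestinal frequency above 0.10 (2.1), so 0.10 is a floor.

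- Expected number at the floor: 40 × 0.10 = 4.
- Chance of at least one: 1 − 0.9^40 = 0.985.
- At an assumed 20% to 30%: 40 × 0.20 = 8 to 40 × 0.30 = 12.

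These count any gastrointestinal effect. They do not count events that need a hold or withdrawal, for which the documents give no rate.

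**Exposure lost by a hold.** Take 3 months as 90 days (assumption). Scheduled metformin is 7 × 1000 + 83 × 2000 = 173,000 mg. A restart with one week at 500 mg twice daily loses a further 7 × 1000 = 7,000 mg.

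- 48-hour hold: (2 × 2000 + 7,000) / 173,000 = 11,000 / 173,000 = 6.4%.
- 7-day hold (assumed length): (7 × 2000 + 7,000) / 173,000 = 21,000 / 173,000 = 12.1%.
- 14-day hold (assumed length): (14 × 2000 + 7,000) / 173,000 = 35,000 / 173,000 = 20.2%.

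**The case against.** A reader might infer something stronger: that 7.10, 8.7 and 13.5 together forbid the investigator from lowering, pausing or stopping the drug for a drug reaction, so that a clinician who acts sensibly breaches the protocol. The documents do not support that.

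- Section 7.10 says when participants will be withdrawn. It does not say that these are the only circumstances.
- N/A also fills 7.8, 7.9 and 8.12, where it means that nothing is specified. It cannot be read as a ban in 8.7, because 8.8 itself tells staff to discontinue metformin around contrast imaging.
- Section 13.5 is aimed at deviations and waivers planned in advance. Stopping a drug because a participant is vomiting is reactive care, which 13.5 does not clearly bar.
- The definitions in 9.1 allow an important medical event to be classed as serious if it needs intervention to prevent a serious outcome. Some cases of drug-related dehydration could then reach criterion 2.

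All of this stands against a claim of prohibition. It does not supply the missing rule: non-exclusive wording is not guidance, and the important-event route depends on individual judgement.

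A reader might also add that the gap biases the primary comparison, because 10.7 analyses only participants with the required drug exposure. That follows from the choice of analysis population and is a separate matter; correcting 7.10 would not remove it. Nor do the counts of gastrointestinal effects show how many participants would be lost.

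**Conclusion.** The point holds as an omission. The written withdrawal criteria leave out non-serious drug-related adverse events, probably by a slip of wording, and no other section gives a routine rule to hold or stop study drug for them. It does not hold as a prohibition on clinical action.

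At least about 4 of 40 participants should have a gastrointestinal effect on metformin, and at least one such participant is close to certain. The number who would need action on study drug is unknown and should be smaller, since section 2.1 says that most cases resolve. The count assumes that the listed frequency carries over to this population and that all 40 reach their metformin period. The correction is worth making because it concerns safety and is cheap, not because a large number of affected participants has been shown.

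**What to change.** 1. **Section 7.10, criterion 3.** Delete the six words that confine it to unrelated events, so that it covers any adverse event requiring withdrawal, whatever the cause.
2. **Section 8.7.** Replace N/A with a hold rule. Study medication is held, with the blind kept and in either arm, while an acute contraindication listed in 6.2, such as dehydration, is present. It restarts with the 8.6 titration once the contraindication has resolved and a repeat check shows stable renal function, which is the condition 8.8 already uses after contrast.
3. **Recording.** Note any hold, and the date of the last dose, at each sputum sample.

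The cost is one deleted phrase and one short paragraph in an amendment, plus the exposure losses calculated above. A hold close to the 3-month sample could dilute the measured effect, which is why the last-dose date is needed. Section 8.6 already requires a starting dose of 500 mg twice daily under the blind, but capsule strength is not stated; that re-titration can use the same units is an assumption to confirm with the supplier.

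A step-down to 500 mg twice daily for intolerance, and any change to the 10.7 population, involve trade-offs about which dose the trial is meant to test. Both are left to the sponsor.

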7.11 Storage and analysis of clinical samples

The samples will all be processed and stored in the laboratories in the Department of Respiratory Medicine at Imperial College, St Mary's campus according to previously established laboratory protocols.

7.12 End of trial

The end of the trial will be the date of the last visit of the last patient undergoing the trial.

8 TRIAL TREATMENTS

8.1 Name and description of investigational medicinal product(s)

The IMP is metformin. The IMP and placebo will be provided by Sharp Clinical Services Ltd (MHRA authorisation number 10284). Metformin and placebo will be packaged in an identical manner. A unique pack ID will be used to identify each pack and its content.

8.2 Regulatory status of the drug

The IMP has a MA in the UK. Repackaging and trial labelling for the trial will be carried out by Sharp Clinical Services Ltd (MHRA authorisation number 10284).

8.3 Product Characteristics

The SmPC for metformin will be provided.

8.4 Drug storage and supply

The IMP will be provided by the supplier (Sharp Clinical Services Ltd) and will be stored at and dispensed from the inpatient pharmacy at St Mary's Hospital. Each subject will be dispensed 1 month's supply when they attend for their baseline visit according to their randomisation code on INFORM. They will then be dispensed 1 month's supply at each of their follow-up monthly visits. Any remaining medication at the end of the study will be collected and counted at the pharmacy who will also be responsible for its destruction.

8.5 Preparation and labelling of Investigational Medicinal Product

The IMP will be prepared and labelled by the supplier. It will be packaged in containers each with 1 month's supply of medication.

8.6 Dosage schedules

The IMP will be commenced at a dose of 500mg twice daily. After 1 week it will be increased to 1000mg twice daily.

8.7 Dosage modifications

N/A

8.8 Known drug reactions and interaction with other therapies

Concomitant use not recommended:

Alcohol. Alcohol intoxication is associated with an increased risk of lactic acidosis, particularly in cases of fasting, malnutrition or hepatic impairment. Therefore any potential participants with excessive alcohol intake (>21 units/week in males and >14 units in females) will not be recruited.

Iodinated contrast agents. Metformin should be discontinued prior to or at the time of the imaging procedure and not restarted until at least 48 hours, provided that renal function has been re-evaluated and found to be stable.

8.9 Concomitant medication

Combinations requiring precautions for use:

Some medicinal products can adversely affect renal function which may increase the risk of lactic acidosis, e.g. NSAIDs, including selective cyclooxygenase (COX) II inhibitors, ACE inhibitors, angiotension II receptor antagonists and diuretics, especially loop diuretics.

Organic cation transporters (OCTs) are active transporters of metformin into the hepatocyte. Drugs that inhibit or induce OCTs have the potential to interfere with the transport of metformin and affect both plasma and intracellular concentrations of metformin. However only a small number of clinically relevant DDIs with metformin have been reported including cimetidine, dolutegravir, pyrimethamine, rifampicin, trimethoprim and verapamil.

If any such products are started during the study, close monitoring of renal function will be carried out.

8.10 Trial restrictions

Women of childbearing potential (WOCBP) are defined according to the Clinical Trial Facilitation Group document (http://www.hma.eu/fileadmin/dateien/Human_Medicines/01-About_HMA/Working_Groups/CTFG/2014_09_HMA_CTFG_Contraception.pdf).

A woman is considered of childbearing potential following menarche and until becoming postmenopausal unless permanently sterile. Permanent sterilisation methods include hysterectomy, bilateral salpingectomy and bilateral oophorectomy. A postmenopausal state is defined as no menses for 12 months without an alternative medical cause. A high follicle stimulating hormone (FSH) level in the postmenopausal range may be used to confirm a post-menopausal state in women not using hormonal contraception or hormonal replacement therapy. However in the absence of 12 months of amenorrhea, a single FSH measurement is insufficient.

WOCBP are required to use adequate contraception for the duration of the trial. This includes:

- 1) Intrauterine Device (IUD)
- 2) Hormonal based contraception (pill, contraceptive injection etc.)

- 3) Double Barrier contraception (condom and occlusive cap e.g. diaphragm or cervical cap with spermicide)
- 4) True abstinence. Sexual abstinence is defined as refraining from heterosexual intercourse during the entire period of risk associated with the study treatments. The reliability of sexual abstinence needs to be evaluated in relation to the duration of the clinical trial and the preferred and usual lifestyle of the subject

8.11 Assessment of compliance with treatment

Subjects will complete a diary card recording medication usage and return any unused medication that will be counted at the monthly visits. Percentage of noncompliance acceptable for a subject to continue in the trial is <80%.

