ISRCTN	International Standard Randomised Controlled Trials Number
MA	Marketing Authorisation

MHRA	Medicines and Healthcare products Regulatory Agency
MS	Member State
NHS R&D	National Health Service Research & Development
NIMP	Non-Investigational Medicinal Product
PI	Principal Investigator
PIC	Participant Identification Centre
PIS	Participant Information Sheet
QA	Quality Assurance
QC	Quality Control
QP	Qualified Person
RCT	Randomised Control Trial
REC	Research Ethics Committee
SAE	Serious Adverse Event
SAM	Synthetic Absorption Matrix
SAR	Serious Adverse Reaction
SDV	Source Data Verification
SOP	Standard Operating Procedure
SmPC	Summary of Product Characteristics
SSI	Site Specific Information
SUSAR	Suspected Unexpected Serious Adverse Reaction
TMF	Trial Master File
TMG	Trial Management Group
TSC	Trial Steering Committee

iii. TRIAL SUMMARY

Trial Title	A pilot, randomised, double-blind, placebo-controlled, cross-over study of metformin to reduce airway glucose in chronic obstructive pulmonary disease (COPD)	
Internal ref. no. (or short title)	A pilot study of metformin to reduce airway glucose in COPD	
Clinical Phase	Exploratory Phase II pilot study	
Trial Design	Randomised, double-blind, placebo-controlled, cross-over	
Trial Participants	Chronic obstructive pulmonary disease (COPD) patients	
Planned Sample Size	40 subjects	
Treatment duration	3 months one study arm, 2 weeks wash out, 3 months in other study arm	
Follow up duration	6.5 months	
Planned Trial Period	24 months	
	Objectives	Outcome Measures
Primary	Effect of metformin on airway glucose	Sputum glucose after 3 months treatment with metformin
Secondary	Effects of metformin on: 1. Glucose levels in the nose 2. Bacterial infection 3. Inflammation in the lung 4. COPD exacerbations 5. Quality of life and symptoms 6. Lung function	1. Glucose levels in nasal SAM strips 2. Bacterial load in sputum 3. Inflammatory markers in sputum 4. Number of COPD exacerbations 5. Quality of life and symptom scores 6. Spirometry
Investigational Medicinal Product(s)	Metformin	
Formulation, Dose, Route of Administration	1000mg bd, po	

iv. FUNDING AND SUPPORT IN KIND

FUNDER(S) (Names and contact details of ALL organisations providing funding and/or support in kind for this trial)	FINANCIAL AND NON FINANCIAL SUPPORT GIVEN
NIHR Imperial Biomedical Research Centre (BRC)	£ 173,511

v. ROLE OF TRIAL SPONSOR AND FUNDER

[figure not shown]

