10 STATISTICS AND DATA ANALYSIS

10.1 Sample size calculation

The primary outcome will be change in sputum glucose from baseline after treatment with metformin, measured using an enzymatic assay (AmplexRed®). The median glucose concentration in COPD subjects measured in our previous study was 1,007 µM (SD 733µM). Metformin reduced airway glucose by c.30% in studies carried out in mice. Therefore to detect a similar effect in humans would require 30 subjects with 90% power at 5% significance. We aim to recruit 40 subjects to account for possible withdrawals.

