10.7 Participant population

The participant populations whose data will be subjected to the trial analysis will be the protocol-compliant population: Any participant who was randomised and received the protocol required trial drug exposure and required protocol processing

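### Section 8.11 accepts noncompliance below 80%, so as written a participant taking just over 20% of doses may continue; the threshold is probably inverted

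*Combined protocol and SAP*

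**What the plan says.** Section 8.11 describes how adherence is measured: "Subjects will complete a diary card recording medication usage and return any unused medication that will be counted at the monthly visits". It then gives the threshold: "Percentage of noncompliance acceptable for a subject to continue in the trial is <80" per cent. This is the only numeric adherence threshold in the protocol.

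The neighbouring sections bear on it as follows.

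- Section 8.6 fixes the dose at 500 mg twice daily for the first week, then: "After 1 week it will be increased to 1000mg twice daily".
- Section 8.7 marks dosage modifications as not applicable.
- Section 7.10 opens with "Participants will be withdrawn from the trial if" and lists three criteria: withdrawn consent, a serious adverse event, and an unrelated adverse event that requires withdrawal. None concerns adherence.
- Section 10.7 defines the analysis population: "Any participant who was randomised and received the protocol required trial drug exposure and required protocol processing". It gives no number for the exposure required.
- Appendix 2 schedules a compliance check at every visit from baseline onwards, in both treatment periods.

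**The concern.** The threshold is attached to the wrong quantity. A limit of 80% is natural as a floor on compliance; here it is written as a ceiling on noncompliance, which lowers the floor to just over 20%.

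The rule is meant to be used. Staff count returned medication each month and need a figure to compare the count with. If they follow the text, they keep a participant who misses three quarters of the doses. If they follow the probable intent and stop someone at 50% adherence, they act against the written protocol, and Section 13.5 does not allow planned deviations or waivers. Section 4 says the pilot is meant to show how large any metformin effect is, so that later trials can be powered. A rule that tolerates about a fifth of the intended exposure does not serve that aim.

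**Working it through.** The 80% is stipulated, not derived, so the plan has no calculation to reproduce. The check is complement arithmetic.

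**Inputs**

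- Threshold: noncompliance below 80% (Section 8.11).
- Two dosing occasions a day (Section 8.6). I count occasions because the documents do not say how many capsules make up a dose.
- Duration (Trial Summary): "3 months one study arm, 2 weeks wash out, 3 months in other study arm". Medication is dispensed monthly (Section 8.4).
- Assumption: the plan gives no day counts, so I take a month as 30 days (range 28 to 31) and a period as 91 days (range 84 to 92).

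**Formulae**

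Let N = 2 × days and m = doses missed.

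- Literal rule: m/N < 0.80, so m is the largest whole number below 0.80 × N, and N − m doses are taken.
- Probable intent: (N − m)/N ≥ 0.80, so the fewest doses taken is 0.80 × N rounded up.

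**Results**

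| Days | N | 0.80 × N | Literal: most missed / fewest taken | At least 80% taken: most missed / fewest taken |
|---|---|---|---|---|
| 28 | 56 | 44.8 | 44 / 12 (21.4%) | 11 / 45 |
| 30 | 60 | 48.0 | 47 / 13 (21.7%) | 12 / 48 |
| 31 | 62 | 49.6 | 49 / 13 (21.0%) | 12 / 50 |
| 84 | 168 | 134.4 | 134 / 34 (20.2%) | 33 / 135 |
| 91 | 182 | 145.6 | 145 / 37 (20.3%) | 36 / 146 |
| 92 | 184 | 147.2 | 147 / 37 (20.1%) | 36 / 148 |

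The conclusion does not depend on the assumed day counts. At the target of 2000 mg a day, the two thresholds correspond to 0.20 × 2000 = 400 mg and 0.80 × 2000 = 1600 mg a day on average.

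A participant who misses 45 of 60 doses in a month has 45/60 = 75% noncompliance. That passes the literal rule and fails an 80% compliance rule by a wide margin.

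**Does another section correct it?** Section 8.6 gives the dose but no tolerance. Section 8.7 plans no dose reduction that could explain so many missed doses. Sections 7.10 and 10.7 carry no adherence figure, and Appendix 2 schedules the check without a criterion. Section 13.5 deals with deviations but sets no threshold.

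**The case against.** The strongest reply is that this is a one-sentence slip which a single site will read as intended, and that gross non-adherence would come to light anyway. Diary cards and monthly counts would show it. Missing most of the prescribed doses is arguably an accidental deviation, which Section 13.5 requires to be documented and reported to the chief investigator and the sponsor. This stands as a limit on the consequences. It does not supply the correct number, and calling the sentence a slip concedes that it needs correcting.

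A second reply is that a lax continuation rule is not in itself a statistical error, since it keeps randomised participants under observation. That is fair, and it is why the fix separates stopping treatment from leaving follow-up.

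Three stronger readings are tempting, and the documents do not support them.

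- A reader might infer that the protocol leaves open what happens to someone who fails the threshold. The sentence is a condition for continuing, so failing it implies not continuing. Only a cross-reference in Section 7.10 and the follow-up arrangements are missing.
- A reader might infer that participants on a fifth of the dose would enter the primary analysis as compliant. Section 8.11 governs continuation, and nothing says that it defines the exposure required by Section 10.7. That undefined term is a separate gap, which would remain if Section 8.11 were worded correctly.
- A reader might try to compute a loss of power from Section 10.1, which says: "Therefore to detect a similar effect in humans would require 30 subjects with 90% power at 5% significance". Such a figure would measure keeping people in or out of the analysis, which Section 8.11 does not decide. It would also need an adherence distribution that the documents do not give, and an allowance for the 10 participants (40 − 30) recruited beyond the required number to cover withdrawals.

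**Conclusion.** The point holds as a minor threshold error: Section 8.11 is wrong as written. The literal meaning is certain. A participant taking just over 20% of doses may continue, which is 13 of 60 in an assumed 30-day month, against at least 48 of 60 under an 80% compliance rule. That the sentence inverts an 80% compliance requirement is an inference, though a likely one, and the sponsor has to confirm it.

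The effect on the primary result is unknown and probably small. The documents do not show how often adherence would fall between the two thresholds, staff may already apply the probable intent, and the rule has no stated link to the analysis population. I therefore attach no power figure to it.

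**What to change.** Reword the last sentence of Section 8.11 along these lines: *Compliance of at least 80% of prescribed doses (noncompliance no more than 20%), assessed cumulatively by pill count at each monthly visit, is required for a subject to continue trial treatment.* The sponsor should confirm the 80%, or give a reason if the lax limit was deliberate. A cumulative monthly check suits a continuation rule. A threshold judged only over a whole treatment period could not be settled until that period had ended.

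Add that participants who fall below the threshold stop trial treatment but stay in follow-up. If the sponsor intends withdrawal from the trial instead, add it as a fourth criterion in Section 7.10.

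The cost is one or two sentences in Section 8.11 and, if withdrawal is intended, one line in Section 7.10. Diary cards and monthly counts are already planned, so no new data collection is needed.
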